**Table 2: Dose Escalation Scheme for the Combination of Oral 5-azacitidine and Romidepsin**

Dose Level	Dose Escalation Schedule		Cycle Length
	Oral 5-azacitidine (Flat dose [mg])	Romidepsin (mg/m  rounded to 14mg/m  )	
Level -1	100 (Days 1-14)	10 (Day 8)	28
Level 1	100 (Days 1-14)	10 (D8 & 15)	28
Level 2	200 (Days 1-14)	10 (Day 8 & 15)	28
Level 3	300 (Days 1-14)	10 (Day 8 & 15)	28
Level 4	300 (Days 1-14)	14 (day 8 & 15)	28
Level 5	300 (days 1-14)	14 (Days 8, 15 and 22)	35
Level 6	300 Days (1-21)	14 (Days 8, 15, 22)	35

**Figure 2: Drug Administration Schema**

#### Dose Levels -1 through 4

Day	1	8	15	22	28

Oral 5-azacitidine	↓	↓	↓	↓	↓	↓	↓	↓	↓	↓	↓	↓	↓	↓
Romidepsin						↓								↓

### Dose Level 5

Day	1	8	15	22	28	35
Oral 5-azacitidine	↓	↓	↓	↓	↓	↓
Romidepsin		↓		↓		↓

### Dose Level 6

Day	1	8	15	21	22	28	35
Oral 5-azacitidine	↓	↓	↓	↓	↓	↓	↓
Romidepsin		↓		↓		↓	

The objective for the dose escalation scheme for Part I is to evaluate the safety and tolerability of various doses of combined oral 5-azacitidine and HDAC inhibition by romidepsin.

Phase II will evaluate the efficacy (ORR) of the MTD of oral 5-azacitidine and romidepsin from Part I in patients with T-Cell Lymphoma. (See figure 2 for study plan flow chart)

### 5.1.2 Regimen Description (Phase 2)

Treatment will be administered on an outpatient basis. Patients will be treated with oral 5-azacytidine and romidepsin at the MTD (i.e the Recommended Phase 2 Dose, or RP2D). The treatment will be administered as follows: oral 5-azacytidine 300 mg (flat dose) Days 1-14 and romidepsin 14 mg/m^2 on Days 8, 15, and 22 on an every 35 day cycle. All patients receiving romidepsin will receive potassium and magnesium supplementation as recommended in the package insert of the product. In all cycles romidepsin will be administered first over 4 hours. Reported adverse events and potential risks for oral 5-azacitidine and romidepsin are described in Section 7. Appropriate dose modifications are described in Section 6. No investigational or commercial agents or therapies other than those described may be administered with the intent to treat the patient's malignancy.

### 5.1.3

#### Required Blood Parameters and Other Investigations Prior to Each Treatment (Except Cycle 1 Day 1)

Before the start of each treatment, patients should be reassessed and the following criteria must be fulfilled:

- ANC > 1000/dL
- Platelet count  $\geq$  50, 000/dL
- Serum creatinine concentration  $\leq 2.0 \times$  ULN or  $\leq$  baseline, or creatinine clearance  $> 50$  ml/min
- AST (SGOT) and ALT (SGPT)  $\leq 2.0 \times$  ULN or  $\leq 3.0 \times$  ULN in presence of demonstrable liver metastases
- Bilirubin concentration  $\leq 2.0 \times$  ULN
- Serum potassium is  $\geq$  institutional LLN and magnesium is  $\geq$  laboratory LLN (supplements must be given to patients whose potassium is < laboratory LLN and/or whose magnesium is < laboratory LLN and serum electrolytes must be rechecked prior to romidepsin administration).
- Recovery of any drug-related non-hematological toxicity to Grade 1 or less, unless otherwise indicated

- ECG schedule as specified in Section 5.1.8.2.

#### 5.1.4

#### Guidelines for Study Drug Administration

- Oral 5-azacitidine will be taken between the hours of 8 and 10 am daily (patient will be required to maintain a drug log recording side effects and time of dosage) on Days 1-14
- Romidepsin will be administered over 4 hours through either a peripheral or central venous catheter on Days 8, 15, 22 of a 35 day cycle. It will be administered within 6 hours of the oral dose. On the day of PK sampling in Cycle 1, the azacitidine will be taken with romidepsin. A dose of the anti-emetic will be administered in accordance with the package insert of romidepsin.
- Administration of the study drugs will be allowed within 48 hours of the scheduled dates.
- Missed doses will not be made up.

#### 5.1.5

#### Maximum Tolerated Dose

The dose-escalation rules and determination of the maximum tolerated dose (MTD) are outlined in Tables 2 and 3. Patients will be enrolled to receive oral 5-azacitidine and romidepsin in sequentially escalating doses until a maximum tolerated dose of the combination has been defined. The maximum tolerated dose of oral 5-azacitidine in combination with romidepsin will be defined as the dose level immediately below the dose level at which greater than or equal to 2 patients out of 6 patients in a cohort experience a dose-limiting toxicity (DLT).

**Table 3: Dose Escalation & De-Escalation Decision Rules:**

Number of Patients with DLT at a Given Dose Level	Escalation Decision Rule
0 out of 3	Enter 3 patients at the next dose level.
1 out of 3	Enter at least 3 more patients at this dose level. If 0 of these 3 additional patients experience DLT, proceed to the next dose level. If 1 or more of this group experience DLT, then dose escalation is stopped, and this dose is declared the maximally administered dose (MAD), and the dose level below is the MTD.
$\geq 2$	Dose escalation will be stopped. This dose level will be declared the maximally administered dose (highest dose administered).
$\leq 1$ out of 6 at highest dose level below the maximally administered dose	This is generally the recommended phase 2 dose. At least 6 patients must be entered at the recommended phase 2 dose.

#### 5.1.6 Dose De-escalation Decision Rules:

If a DLT is reached in the first cycle for a given patient, then the previous dose level will be utilized for that particular patient in subsequent cycles. Should that patient experience a second DLT at that lower dose, they will be removed from the study. Dose-escalation will resume until the maximally administered dose is achieved or MTD is reached.

For example, according to the schema in Table 2, if DLT is reached at dose level 1 (romidepsin 10 mg/m^2 and oral 5-azacitidine 100 mg/m^2), the frequency of romidepsin will be reduced to a Day 8 only dose. Dose escalation can resume starting at that point according to dose escalation rules (Table 3). The same

applies if DLT is reached at all other levels prior to dose level four.

Toxicities in cycles 2 and following may be accommodated by treating patients at one dose level below the present cohort. Toxicity in cycles 2 and beyond will not affect dose escalation for future patients.

In the Phase 2, de-escalation should follow the Phase 1 escalation guidelines. For instance, any recurrent Grade 3 toxicity, up to 3 de-escalations will be allowed, with the doses of the drugs being reduced to that described in Cohort 5 (azacytidine 300 mg Day 1-14, and romidepsin 14 mg/m^2 Day 8 and 15 every 28 days) → Cohort 4 (azacytidine 300 mg Day 1-14, and romidepsin 10 mg/m^2 Day 8 and 15 every 28 days) and then Cohort 3 (azacytidine 200 mg Day 1-14, and romidepsin 10 mg/m^2 Day 8 and 15 every 28 days). Any patient experiencing a Grade 4 toxicity should just be immediately dose reduced according to the guideline above. In addition, patients can be dose reduced per the treating physicians discretion.

Specifically, for hematologic toxicities, patients may receive GCSF for neutropenia. For cases where patients miss a dose secondary to a recurrent Grade 3 ANC or platelet count, or Grade 4 hematologic toxicity, dose reductions should occur as noted above at the physicians discretion (i.e. reduce to Cohort 5, then 4 then 3).

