## **5.2 Dose-Limiting Toxicity**

A dose limiting toxicity (DLT) is defined as any toxicity not specifically included in section 5.2 that occurs within cycle 1 and is considered at least "possibly related to study drug administration." DLT is also defined as any toxicity possibly related to drug, occurring up to 7 days after completion of cycle 1 that results in a delay of initiating cycle 2. For patients who discontinue study drug administration after Cycle 1, DLT will be defined as any toxicity not specifically included in section 5.2 that occurs within 30 days of the last dose of drug on study, in cycle 1 that is considered at least possibly related to study

drug.

DLTs include:

- Hematologic dose-limiting toxicity will be defined as either Grade 4 neutropenia that does not resolve to  $\leq$  Grade 2 within  $\leq$  7 days, any Grade 4 thrombocytopenia, or any Grade 5 hematologic toxicity. At least three patients in each cohort must be evaluable for hematologic toxicity.
- Non-hematologic dose-limiting toxicity will be defined as any Grade 3, 4 or 5 non-hematologic toxicity, with the specific exception of:
- Grade 3 nausea or Grade 3 vomiting that in the opinion of the investigator occurs in the setting of inadequate compliance with supportive care measures specified in Section 5.1.7 and lasts for less than 48 hours.
- Grade 3 diarrhea that in the opinion of the Investigator occurs in the setting of inadequate compliance with supportive care measures specified in Section 5.1.7 and lasts for less than 48 hours.
- Grade 3 dehydration that, in the opinion of the investigator, occurs in the setting of inadequate compliance with supportive care measures specified in Section 5.1.7 and lasts for less than 48 hours.
- Grade 3 acidosis or alkalosis that responds to medical intervention by returning to  $\leq$  Grade 2 within 48 hours.
- Isolated (i.e. no other abnormalities) Grade 3 elevation of liver function tests (LFTs) without associated clinical symptoms, lasting for  $\leq$  5 days in duration.
- Isolated (i.e. no other abnormalities) Grade 3 elevation of amylase without associated clinical symptoms, lasting  $\leq$  5 days
- Grade 3 hypocalcemia, hypokalemia, hypomagnesemia, hyponatremia, or hypophosphatemia that responds to medical intervention.
- Grade 3 hypercholesterolemia.
- Grade 3 hypertriglyceridemia
- Grade 2 Alopecia
- Grade 3 Constipation
- Grade 3 Fatigue

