#### Romidepsin dose modification for Other Non-Hematologic and Hematologic Toxicities

All previously established or new toxicities observed any time, with the exception of those mentioned above, are to be managed as summarized in Table 8:

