**TABLE 8: Dose Modifications for Romidepsin**

Dose Modifications for Romidepsin	
CTCAE Grade or Abnormal Value	Romidepsin
Thrombocytopenia	
Grade 1 ( $75 \times 10^9/L - < LLN$ ) Grade 2 ( $50 - < 75 \times 10^9/L$ )	Maintain dose level Maintain dose level
Grade 3 or 4 thrombocytopenia:  OR  Thrombocytopenia that requires platelet transfusion or recurrent Grade 3 or 4 thrombocytopenia	Hold subsequent doses of therapy until thrombocytopenia returns to $\leq$ Grade 2 or baseline and continue at full dose  Hold subsequent doses of therapy until thrombocytopenia returns to $\leq$ Grade 2 or baseline and permanently reduce dose of romidepsin to the next reduced level below.. If the same toxicity recurs despite dose reduction, patients should be taken off study.
Neutropenia (ANC)	
Grade 1 ( $1.5 \times 10^9/L - < LLN$ ) Grade 2 ( $1.0 - < 1.5 \times 10^9/L$ )	Maintain dose level Maintain dose level
Grade 3 and 4 neutropenia:	Hold subsequent doses of therapy until specific cytopenia returns to $\leq$ Grade 1 or baseline and continue at full dose
Febrile Neutropenia	
Febrile ( $\geq 38.5^{\circ}C$ ) Grade 4 neutropenia or recurrent Grade 3 or 4 neutropenia:	Hold subsequent doses of therapy until neutropenia returns to $\leq$ Grade 1 or baseline and permanently reduce dose of romidepsin to the next reduced level below.. If the same toxicity recurs despite dose reduction, patients should be taken off study
All Other Non-Hematologic Drug Toxicities (not mentioned in previous tables)	
Grade 1 or 2:	Maintain dose level
Grade 3	Hold treatment with romidepsin until toxicity returns to $\leq$ Grade 1 or baseline, then restart therapy at full dose. If Grade 3 toxicity recurs, reduce dose of romidepsin to the next reduced level below.. This is a permanent dose reduction.
Grade 4	Grade 4 toxicity: Hold treatment with romidepsin until toxicity returns to $\leq$ Grade 1 or baseline, and then restart therapy at the next reduced level below.. This is a permanent dose reduction

Dose interruption or study discontinuation is not required for lymphopenia of any grade.

In general, if study drug has been held and the toxicity does not resolve, as defined above, then drug must

be discontinued.

Note: Dose reductions should not be performed for alopecia or for nausea or vomiting that was not treated with aggressive anti-emetic support.

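### When the same cytopenia recurs after one dose reduction in Phase II, Section 5.1.6 allows further reductions, Table 8 takes the patient off study, and nothing says which governs

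*Combined protocol and SAP*

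**What the plan says.** Section 5.1.6 states for Phase II: "any recurrent Grade 3 toxicity, up to 3 de-escalations will be allowed". It lists three successive reduced regimens. A separate hematologic paragraph covers a dose missed because of a recurrent Grade 3 neutrophil or platelet count, or a Grade 4 hematologic toxicity: "dose reductions should occur as noted above at the physicians discretion (i.e. reduce to Cohort 5, then 4 then 3". Neither paragraph has an off-study step.

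Table 8 in Section 6.3.1 (a different table in Section 7.4.2 has the same number) is introduced as covering "All previously established or new toxicities observed any time", apart from the cardiac findings dealt with just before it. For thrombocytopenia that is recurrent at Grade 3 or 4, or needs transfusion, it requires a hold and a permanent romidepsin reduction, and then: "If the same toxicity recurs despite dose reduction, patients should be taken off study". The same sentence appears in the Febrile Neutropenia row, whose trigger includes the words "Grade 4 neutropenia or recurrent Grade 3 or 4 neutropenia".

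Section 5.1.2 (the Phase II regimen) and the close of Section 5.2 send the reader to Section 6 for dose modification. The thrombocytopenia item in Section 5.1.7 sends the reader to Section 6.3. Section 6.3 offers the romidepsin package insert or, as an alternative, the escalation and de-escalation tables.

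**The concern.** The two texts address the same event in the same patient and differ on whether treatment goes on. One grants further reduced regimens and the other ends participation. These are safety instructions, so the treating physician should not have to choose between them.

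The event is foreseeable. Section 2.4.2 reports Grade 3/4 thrombocytopenia and febrile neutropenia in 19.2% each of the 26 Phase I patients (5/26 = 19.2%), all dose levels combined. The same section says patients at the MTD had no toxicities, so these figures do not give a Phase II frequency. The primary endpoint is best response within four cycles (Section 13.3) in 24 patients (Section 13.2), so a rule on stopping treatment can bear on how much treatment a patient receives before that assessment.

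**Working it through.** The plan gives no figure to reproduce. The check follows one Phase II patient with Grade 3 thrombocytopenia, no transfusion, and a missed dose at each recurrence.

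| Event | Section 5.1.6, Phase II text | Table 8, Section 6.3.1 |
|---|---|---|
| First episode | Ladder not yet triggered | Hold, then full dose |
| Recurrence at full dose | Step 1 (its Cohort 5) | Hold, then one permanent romidepsin reduction |
| Recurrence after that reduction | Step 2 (its Cohort 4) | Off study |
| Next recurrence | Step 3 (its Cohort 3) | Not reached |

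The rules part at the third row. Steps left at that point are 3 − 1 = 2 under Section 5.1.6 and 1 − 1 = 0 under Table 8.

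Planned romidepsin per week (dose × infusions ÷ weeks per cycle) shows what the remaining steps contain:
- Phase II regimen (Section 5.1.2): 14 × 3 ÷ 5 = 8.4 mg/m².
- Step 1: 14 × 2 ÷ 4 = 7.0 mg/m².
- Steps 2 and 3: 10 × 2 ÷ 4 = 5.0 mg/m², and 5.0 ÷ 8.4 = 59.5% of the Phase II regimen.

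At the branch, one text therefore allows a planned 5.0 mg/m² per week and the other allows no treatment. These are planned schedules without delays, not measures of harm.

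**Neutropenia.** The plain neutropenia row of Table 8 has no recurrence rule. The off-study sentence is in the febrile row, and it is not clear whether the fever condition also qualifies the recurrent Grade 3 or 4 neutropenia named there. The conflict is explicit for platelets only.

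**Precedence.** Sections 5.1.2, 5.1.7 and 5.2 lead to Section 6. Section 6.3 leads either out to the package insert or back to the escalation tables. The labels do not match those tables either: the regimen that Section 5.1.6 calls Cohort 5 is Level 4 in Table 2, and Level 5 in Table 2 is the full Phase II regimen.

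**Secondary: first Grade 4 cytopenia without fever or transfusion.** A general sentence in Section 5.1.6 calls for immediate reduction. Its hematologic paragraph leaves reduction after a missed dose to discretion. Table 8 says to hold and then continue at full dose.

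**Secondary: neutrophil recovery.** The threshold is Grade 2 or less in Sections 6.1 (for DLTs) and 6.2, ANC above 1000 in Section 5.1.3, and Grade 1 or baseline in Table 8. Reading the printed unit in Section 5.1.3 as per microlitre (an assumption), a count above 1.0 but below 1.5 × 10⁹/L passes the first three but not Table 8, unless baseline was that low. A count of exactly 1.0 fails Section 5.1.3, whose limit is strict.

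**The case against.** The best defence is that Section 5.1.6 only permits further steps. A physician who stops treatment breaches neither text, and both texts lower exposure after a recurrence. That stands as far as it goes. It does not reconcile the rules: a physician who uses the permission departs from Table 8, and discretion does not say which text prevails. Nor does it help that Table 8 is titled for romidepsin, because going off study ends both drugs.

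Several stronger readings are tempting, but the documents do not support them:
- **Different sites acting differently.** No second site is described. Section 13.1 calls Phase I single-institution, and the number of Phase II sites is not stated. The text supports only a difference between physicians.
- **No reductions at all for a DLT**, because Section 5.4 lists DLTs among reasons to end treatment. That is a generic list, and this reading would cancel both Section 5.1.6 and Table 8.
- **Removal at a second DLT in Phase II.** Section 5.1.6 opens with "Should that patient experience a second DLT at that lower dose, they will be removed from the study" and later says "In the Phase 2, de-escalation should follow the Phase 1 escalation guidelines". The DLT definition in Section 5.2 includes "any Grade 4 thrombocytopenia". But the removal sentence follows from a first-cycle DLT during dose escalation, Section 5.2 ties DLTs to cycle 1 and short windows after it, and the Phase II sentence is illustrated at once by the three-step ladder. Its reach into Phase II is uncertain.
- **A forced conflict at the first Grade 4 cytopenia.** The hematologic paragraph can be read as qualifying the general sentence, and full-dose resumption under its discretion then agrees with Table 8.
- **Contradictory neutrophil thresholds.** Section 5.1.3 sets minimum conditions, Section 6.2 is permissive, and Section 6.1 concerns DLTs. Waiting for Table 8's level meets all of these thresholds, so they need aligning but do not exclude one another.

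**Conclusion.** The conflict is real and should be corrected. For thrombocytopenia recurring after one reduction in Phase II, Section 5.1.6 leaves two further steps and Table 8 leaves none, and no text states precedence. For neutropenia the same conflict arises only if the off-study sentence covers recurrence without fever, which the table does not settle.

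This rests on Table 8 applying in Phase II, as its introduction and the pointer from Section 5.1.2 indicate, and on the same toxicity recurring. The three steps in Section 5.1.6 could also be used for different toxicities, where the comparison of three with one does not apply.

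A reader might infer that the conflict biases the response rate. The documents give no Phase II frequency of recurrent cytopenia and no basis for estimating that effect, so no such claim is made. The Grade 4 and neutrophil-recovery points are secondary matters of clarification.

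**What to change.** Reconcile Section 5.1.6 with Table 8 in Section 6.3.1, and bring the pointers in Sections 5.1.2, 5.1.7, 5.2 and 6.3 into line, so that one named source governs recurrent cytopenia in Phase II. State whether the off-study sentence in the Febrile Neutropenia row covers recurrence without fever, and whether removal at a second DLT applies in Phase II. Align the wording for a first Grade 4 cytopenia and for neutrophil recovery across Sections 5.1.3, 5.1.6, 6.1, 6.2 and Table 8. If physician discretion is meant to remain, say where it applies.

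The investigator and sponsor decide which rule is intended; this review takes no position on that. The cost is amendment wording only, with no change to sample size or analysis.

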## 6.3 Dose Modifications

If oral 5-azacitidine and romidepsin administration leads to a DLT beyond cycle 1 at a given dose level, dose modifications will occur in accordance with the drugs' FDA approved package insert for romidepsin, or as outlined in the dose (de)escalation tables. These post Cycle 1 DLTs will not count towards the overall determination of MAD & MTD for this study.

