## 7.2 Comprehensive Adverse Events and Potential Risks Lists (CAEPRs)

### 7.2.1 CAEPRs for Oral 5-azacitidine

### **7.2.1.1 Clinical Trials Experience**

In Study AZA-001 and Studies 8921/9221 with SC administration of azacitidine, adverse reactions of neutropenia, thrombocytopenia, anemia, nausea, vomiting, diarrhea, constipation, and injection site erythema/reaction tended to increase in incidence with higher doses of azacitidine. Adverse reactions that tended to be more pronounced during the first 1 to 2 cycles of SC treatment compared with later cycles included thrombocytopenia, neutropenia, anemia, nausea, vomiting, injection site erythema/pain/bruising/reaction, constipation, petechiae, dizziness, anxiety, hypokalemia, and insomnia. There did not appear to be any adverse reactions that increased in frequency over the course of treatment. Overall, adverse reactions were qualitatively similar between the IV and SC studies. Adverse reactions that appeared to be specifically associated with the IV route of administration included infusion site reactions (eg, erythema or pain) and catheter site reactions (eg, infection, erythema, or hemorrhage).

In general, the most common AEs reported during the azacitidine clinical trials reflect the underlying nature of the disease and the cytotoxic properties of azacitidine. No clinically significant differences were seen when the safety data were analyzed for age, gender, or MDS subtypes.

Of the most frequently occurring adverse reactions ( $\geq 20\%$ ) in azacitidine-treated patients during the AZA-001 study, the majority was transient, non-serious, and resolved during the study.

These most common adverse reactions can be managed through delays or dose decrease of azacitidine and concomitant treatment. Further details are provided below.

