#### **Hematological Events**

The most commonly reported adverse reactions associated with azacitidine treatment were hematologic events, including anemia, thrombocytopenia, neutropenia, and leukopenia. Bone marrow failure or pancytopenia were also reported less frequently. Complete blood counts should be performed at baseline, prior to administration of each dosing cycle, and whenever deemed clinically necessary to monitor potential toxicity or response. After administration of the recommended dosage for the first cycle, dosage for subsequent cycles should be adjusted. There is a greater risk of these events occurring during the first 2 cycles, after which they occur with less frequency in patients with restoration of hematological function. Most hematological adverse reactions were managed by routine monitoring of CBCs and delaying azacitidine administration in the next cycle, prophylactic antibiotics and/or growth factor support (eg, granulocyte colony stimulating factor [G-CSF]) for neutropenia and transfusions for anemia or thrombocytopenia as required.

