## **Gastrointestinal Events**

Nausea and vomiting are common AEs that accompany therapy with azacitidine, especially following high doses administered rapidly by IV bolus. During the CALGB clinical trials, nonsteroidal antiemetics were used to counteract these AEs and allowed the continuation of azacitidine therapy. The majority of patients received prochlorperazine or a 5-HT3 receptor antagonist (eg, granisetron, ondansetron). During Study AZA-001, antiemetic therapy for nausea/vomiting most commonly included metoclopramide, ondansetron, or domperidone. Constipation has also been commonly reported during treatment with azacitidine and may be a consequence of the recommended antiemetic pre-treatment. During Study AZA-001, if treated, constipation was most commonly managed with stool softeners and/or laxatives (eg, lactulose and coloxyl with senna).

Diarrhea is also a commonly reported adverse event associated with azacitidine therapy. Diarrhea may be more frequent and/or more severe in patients receiving orally administered azacitidine. It is recommended that patients experiencing diarrhea associated with azacitidine be managed according to the publication in the Journal of Clinical Oncology (Benson, 2004). A dose reduction of oral azacitidine may be appropriate based on the severity of diarrhea observed and the response to treatment intervention.

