#### 7.2.2.1 Clinical Trials Experience

In a study with 71 patients, the median number of administered cycles was four (1-to 72 cycles). Among the administered doses 76% were full doses, 7% were escalated doses, and 17% were reduced doses. Eight doses were held; three doses in three patients were held as a result of thrombocytopenia (< 50 x 10^9/L), two were held for persistent grade 3 nausea, and three were held as a result of persistent grade 3 fatigue[4].

Common nonhematologic adverse effects (any grade) included fatigue (41%), nausea (52%), vomiting (20%), and anorexia (21%). Hematologic abnormalities included leukopenia (31%), granulocytopenia (37%), lymphopenia (21%), thrombocytopenia (39%), and anemia (37%). Transient elevations of liver function tests, AST or ALT, were observed in 13 patients; two additional patients had isolated grade 1 hyperbilirubinemia. Hyperuricemia was noted in 11 patients (eight patients with grade 1 and three patients with grade 3), and hypophosphatemia was noted in six different patients. ECG changes were noted consisting of asymptomatic T-wave flattening (71%) or ST segment depression (9%). Toxicities in later cycles mirrored those observed in the first cycle. Infections occurred in 38 patients (54%) over 58 cycles (11%), including bacterial infections of the skin and upper respiratory, pulmonary, GI, and urinary tracts; bacteremia; and sepsis, and were not related to neutropenia[4].

The most common AEs reported among subjects who received romidepsin monotherapy include GI disturbances (nausea, vomiting, constipation, diarrhea), hematologic toxicities (anemia, thrombocytopenia, neutropenia), and asthenic conditions (fatigue, asthenia, lethargy). Other types of events commonly seen with romidepsin include anorexia, clinical chemistry abnormalities (hypocalcemia, hypoalbuminemia, hyperglycemia, and hypomagnesemia), pyrexia, and taste disturbances.

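### Steps 1 and 2 of the Phase II reduction ladder lower romidepsin but raise planned azacitidine by 25% per day, and no azacitidine reduction is written before step 3

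*Combined protocol and SAP*

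**What the plan says.** Section 5.1.2 sets the Phase II dose (RP2D): azacitidine 300 mg on Days 1-14 and romidepsin 14 mg/m² "on Days 8, 15, and 22 on an every 35 day cycle".

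Section 5.1.6 allows up to three reductions for recurrent Grade 3 toxicity. The first has the "doses of the drugs being reduced to that described in Cohort 5 (azacytidine 300 mg Day 1-14", with romidepsin 14 mg/m² on Days 8 and 15. The second keeps azacitidine and lowers romidepsin to 10 mg/m². The third lowers azacitidine to 200 mg with romidepsin 10 mg/m². All three repeat every 28 days. For Grade 4 the rule is: "Any patient experiencing a Grade 4 toxicity should just be immediately dose reduced according to the guideline above". The section also lets the treating physician reduce at discretion. It gives the same order of steps for hematologic toxicity.

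Section 6.3 adds no azacitidine step. It refers to the "FDA approved package insert for romidepsin, or as outlined in the dose (de)escalation tables", and the modification tables in 6.3.1 (Tables 7 and 8) are written for romidepsin.

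Elsewhere the protocol expects that azacitidine itself may need changing:

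- Section 7.2.1.1, drawing mainly on subcutaneous data: "These most common adverse reactions can be managed through delays or dose decrease of azacitidine and concomitant treatment".
- Hematological Events, on how most such reactions were managed, among other measures: "delaying azacitidine administration in the next cycle".
- Gastrointestinal Events: "A dose reduction of oral azacitidine may be appropriate based on the severity of diarrhea observed and the response to treatment intervention".
- Section 5.1.7 says mucositis and hepatotoxicity on azacitidine may call for a dosage change.

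**The concern.** A reduction step should not plan more of the drug that may have caused the toxicity. Steps 1 and 2 leave the azacitidine course unchanged and bring the next one forward by 7 days. That suits a patient whose toxicity comes from romidepsin. For a patient with diarrhea, mucositis or cytopenia from azacitidine, the written plan goes the wrong way for that drug until step 3.

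Some patients may never reach step 3. Table 8 in 6.3.1 takes a patient off study if certain cytopenias recur after one romidepsin reduction. Where that rule is applied, a patient could leave treatment without ever having been planned for less azacitidine.

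**Working it through.** The documents state no dose-intensity figure, so there is none to reproduce. The measure here is planned dose per calendar day: dose × administrations per cycle ÷ cycle length. Inputs are from 5.1.2 (RP2D) and 5.1.6 (steps).

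| Regimen | Azacitidine, mg/day | v RP2D | Romidepsin, mg/m²/day | v RP2D |
|---|---|---|---|---|
| RP2D, 35 days | 300×14/35 = 120 | – | 14×3/35 = 1.20 | – |
| Step 1, 28 days | 300×14/28 = 150 | +25% | 14×2/28 = 1.00 | -17% |
| Step 2, 28 days | 300×14/28 = 150 | +25% | 10×2/28 = 0.71 | -40% |
| Step 3, 28 days | 200×14/28 = 100 | -17% | 10×2/28 = 0.71 | -40% |

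Azacitidine per cycle is 4,200 mg at the RP2D and at steps 1 and 2, and 2,800 mg at step 3. Over 140 days the plan is 120×140 = 16,800 mg at the RP2D, 21,000 mg at steps 1 and 2, and 14,000 mg at step 3.

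**Rest periods.** Azacitidine-free days per cycle fall from 35-14 = 21 to 28-14 = 14. Days free of both drugs stay at 13 (Days 23-35 at the RP2D, Days 16-28 on the ladder).

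**Delays.** The documents give no delay rate, so the delay d per cycle is an assumption.

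- Only the reduced cycles are delayed, 4,200/(28+d) against 120: d = 3 gives 135.5 (+13%), d = 7 gives 120 (0%), d = 14 gives 100 (-17%).
- The same delay applies before and after reduction, (35+d)/(28+d): d = 3 gives +23%, d = 7 gives +20%, d = 14 gives +17%.

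**Missed doses.** These are not made up (5.1.4). The rise is cancelled when 14 - 120×28/300 = 2.8 doses are missed per 28-day cycle, about 3.

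**Phase I (2.4.2).** Two comparisons point in different directions.

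- Azacitidine 200 mg Days 1-14 with romidepsin 10 mg/m² twice every 21 days averaged 200×14/21 = 133 mg/day and 20/21 = 0.95 mg/m²/day, with 6 days free of both drugs, and had two DLTs. Step 1 averages more of both drugs (150 and 1.00) with 13 such days, yet escalation went past it.
- The maximum administered dose changed only azacitidine from the RP2D: 300×21/35 = 180 mg/day, again with 13 days free of both drugs. It had two Grade 4 hematologic DLTs.

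**The case against.** The strongest case on the other side has four parts.

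**The protocol already provides delay.** Section 6.1 holds the study drugs for a DLT until it returns to Grade 2 or less, and stops treatment if the interruption exceeds 14 days. Section 5.1.3 requires recovered counts, and drug-related non-hematologic toxicity at Grade 1 or less, before each treatment. A patient who has not recovered should not start the next course on Day 29. This stands, and it limits the delivered increase. It does not help a patient who recovers in time and then receives the same 300 mg course a week sooner.

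**Discretion.** Section 5.1.6 lets the physician reduce as judged necessary. This also stands, but no azacitidine dose is defined for that purpose, and the named order puts azacitidine last.

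**Romidepsin may be the cause.** Thrombocytopenia occurred in 39% of patients in the romidepsin study (7.2.2.1) and led to 33 of its 42 protocol-mandated dose reductions (7.2.2.6). Cutting romidepsin first is defensible when it is the likely cause. The point is therefore confined to toxicity that may come from azacitidine.

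**The measure and the evidence.** Average mg/day is not a protocol target, and neither the daily nor the per-cycle azacitidine dose rises. Steps 1 and 2 are regimens that Phase I escalated past. A reader might infer that these steps are more toxic than the RP2D. The documents do not show that: romidepsin falls, the rest from both drugs is unchanged, and the Phase I comparisons are mixed and rest on very few patients.

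**Conclusion.** The point holds as a gap in the dose-modification rules and is worth considering. Planned azacitidine rises 25% at steps 1 and 2 and falls below the RP2D only at step 3, although the protocol says an azacitidine reduction may be needed.

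The 25% is exact for planned dose over calendar time, assuming cycles run on schedule with no missed doses. It should not be read as the delivered increase. Under the delay assumptions above, the change ranges from +23% to -17%.

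No effect on the response rate, sample size or any analysis is shown. The cohort labels are a clerical matter: 5.1.6 follows the numbering in 2.4.2, whereas the synopsis uses Dose Cohort 5 for the 35-day regimen. Because 5.1.6 writes each regimen out, the intended doses are clear.

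**What to change.** Add one option to 5.1.6. For toxicity judged at least possibly due to azacitidine (for example diarrhea, mucositis, or Grade 4 or recurrent Grade 3 cytopenia), allow as the first step azacitidine 200 mg Days 1-14 with romidepsin 14 mg/m² Days 8 and 15 every 28 days. Keep the existing ladder for romidepsin-type toxicity.

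Planned azacitidine is then 200×14/28 = 100 mg/day and romidepsin 14×2/28 = 1.00 mg/m²/day, both 17% below the RP2D. Romidepsin is exactly as in the present step 1, the 13 days free of both drugs are kept, and neither drug exceeds Level 4 of Table 2.

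The cost is one amended paragraph, with no change to starting dose or sample size. In the patients concerned, azacitidine per cycle falls from 4,200 to 2,800 mg, which may cost activity. The exact combination is not a listed Table 2 level.

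Keeping a 35-day cycle at every step is a weaker choice. It removes the rise, but azacitidine would be 120, 120 and 80 mg/day, so there is still no reduction before step 3. Romidepsin would fall by 33% (28/35 = 0.80 mg/m²/day) and then 52% (20/35 = 0.57).

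Naming the steps by regimen would settle the labels in the same edit.
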